Research has shown that a successful implementation depends on interplay between the effectiveness of the implementation strategies chosen to support the implementation and characteristics of the implementation object, the implementers, the target population and the context of the implementation (Table 1).

Updated design of the implementation research

The project was planned to be conducted using a cross-over design in two counties in south of Sweden based on a feasibility/pilot study that was conducted during fall 2014 *co-created palliative care educational intervention through seminars for professionals in nursing homes*. Due to a more significant amount of drop-outs compared with expected (and for not receiving the total amount of applied foundation), the plan needed to be revised. The knowledge-based palliative care intervention was conducted as a non-randomized control trial, implemented over a six-month period in 30 nursing homes in two different counties in the south of Sweden (County A and County B). The data collection was made in two sequential periods in each county. First, the intervention was implemented in ten nursing homes in County A (Kronoberg County from April 2015), while ten nursing homes in County B served as a control group. Then, County B implemented the intervention (Skåne county from August 2016), and ten new nursing homes in County A, which had not received the intervention, were chosen as a control group. After the two sequential time periods were data from one intervention and one control group analysed. The selection through voluntary participation resulted in a mixture of both larger and smaller nursing homes within the two counties (cluster samples), as well as both from urban and rural areas.

Implementation object

According to the National Board of Health and Welfare, palliative care should be based on four cornerstones: symptoms relief, multi-professional cooperation, communication and relation as well as support to the next of kin (Socialstyrelsen 2012). The aim of palliative care is to reduce suffering and promote the quality of life for patients with progressive, incurable illnesses or injuries. The care should address physical, psychosocial and spiritual needs as well as provide support to the next of kin. The definition by the National Board of Health and Welfare closely

adheres to the definition of palliative care by the World Health Organization (WHO), (Socialstyrelsen 2013).

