The evaluation consist of 8 studies and involves four implementation outcomes in accordance with the framework proposed by Proctor *et al.* (2011): **Acceptability** - The perception among implementers (nursing home staff and managers) that a given knowledge-based practice (palliative care in nursing homes) is agreeable, towards benefit or satisfactory; **Appropriateness** - The perceived fit, relevance or compatibility of an knowledge-based practice (palliative care), for a given practice setting, provider, or consumer (older persons and their next of kin); **Feasibility** - The extent to which an knowledge-based practice (palliative care) can be successfully used or carried out within a given agency or setting (nursing homes); and **Fidelity** - The degree to which an knowledge-based practice (palliative care in nursing homes) was implemented as it was prescribed in the original protocol (the knowledge documents concerning palliative care).

Participants in studies

The persons asked for participation in this study, i.e. older persons, next of kin, staff and leaders are recruited from the included nursing homes in both Skåne and Kronoberg counties. The persons are selected consecutively until the stipulated figures are reached (Table 2).

Methods and instruments

The following methods and instruments will be used in this project:

Questionnaires

Quality of life: The WHOQOL-BREF questionnaire (WHO, Manual 1996) and the WHOQOL-OLD questionnaire (WHO, Manual 2006) assessed quality of life. The older persons and next of kin will answer to the questions in a structured interview. The WHOQOL-BREF is often used together with the WHOQOL-OLD module and both are psychometric tested by the WHOQOL Group (Power *et al.*, 1999). The WHOQOL-OLD module have been validated for old people in several countries, for example Sweden (Power *et al.* 2005) and can be used in a wide variety of studies including cross cultural investigations, population epidemiology, health monitoring, service development, and clinical intervention trials in which issues about quality of life are crucial (WHO, Manual 2006). The project has acquired permissions from WHO to use these questionnaires and in order to make it easier to answer the questionnaires, the answer alternatives will be enlarged on a separate paper and used during the interview.

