Official title of the study:
Implementation of Knowledge-Based Palliative
Care for Frail Older Persons in Nursing Homes

NCT number: NCT02708498

Date of the document: April 8, 2015, updated October 6, 2020

Statistical Analysis Plan

Simple descriptive statistics:

Median-Mean, Quartiles, Percentage

These are applied to all quantitative studies.

Baseline study:

Target population: Older people

Instruments: Characteristics of older participants, WHOQOL-BREF & WHOQOL-OLD

The data were analysed in one descriptive and one analytical section. In the descriptive section, numbers and percentages were calculated on a group level. A mean score was calculated for each domain using both the raw domain score, a standardized domain score (SDS) with the raw domain score divided by the number of items in the domain (1-5) and a transformed domain mean score (TDS 0-100) according to the instrument manuals. The different calculations were performed to enable comparison of our results with those from other studies.

In the analytical section, the participants were divided into two age groups (66-88 years and 89-102 years) by the population median age and gender (female and male). To examine differences in quality of life, a comparison of medians was conducted using the Mann-Whitney U test.

Comparative studies (Baseline and Follow-up):

Target population: Older people, next-of-kin, staff

Instruments: PCAT, PCQ-S, PCQ-P, WHOQOL-BREF, WHOQOL-OLD, Your experience of palliative care, Next-of-Kin Participation in Care (NoK-PIC)

The selection of the statistical tests to analyze data other than the descriptive statistics was based on whether the data were distributed normally and the scale level of the instruments. The Mann-Whitney U-test and the Kruskal-Wallis test was applied to compare the baseline characteristics of the two groups. The quantitative data collected from questionnaires were analyzed using within-group comparisons (the data from after the intervention period were compared with the data from before the intervention period in the intervention group and the control group) by Wilcoxon signed rank test.

Either Pearson's chi-square test or Fisher's exact test was used when the expected value was less than 5.

A two-tailed p-value of <0.05 was regarded as statistically significant.

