In order to investigate if the drop-outs consisted a threaten of external validity we performed sub-groups analysis through comparing the drop-outs in the intervention group with the participants in the intervention group, and comparing the drop-outs within the control group with the participants in the control group.

Analyses were performed using IBM SPSS Statistics version 24.

Logistic regression studies (Baseline and Follow-up):

Target population: Staff
Instruments: P-CAT, PCQ-S

A univariate logistic regression analysis was performed with the independent variable improvement/non-improvement in P-CAT and PCQ-S and the dependent variable group (control/implementation).

Psychometric studies

Target population: Next-of-kin
Instrument: Next-of-Kin Participation in Care (NoK-PiC)

Step 1. Dimensionality

The dimensionality of the 37 items was explored by means of Rasch Model Analysis (RMA) and Explorative Factor Analysis (EFA). EFA needs complete data, i.e. no missing responses in any items. RMA can process missing data. Estimation methods merely summarize the non-missing observations that are relevant, and compare them with their expectations.

NoK-PiC data was analysed according to Rasch Measurement Theory (RMT), using the polythomous Rasch model in RUMM2030 (Professional Edition 5.4). A principal component analysis of the residuals was conducted in RUMM2030 to explore dimensionality of the NoK-PiC items. Person location estimates were derived from subsets of items that loaded positively and negatively on the first principal component of residuals. The overall proportion of persons with significantly different measures from the two item subsets should be <5% to support unidimensionality.

EFA was conducted based on recommendations including parallel analysis to decide for decision about how many factors to retain for rotation, Minimum Rank Factor Analysis (MRFA, that is able to estimate the percentage of common variance explained by the EFA model), and on a promine rotation that allows factors to correlate (oblique). In addition, since the items are polythomous, and since MRFA assume only minor departures from normality, we based the analysis on a polychoric correlation matrix. The software FACTOR (Lorenzo-Seva, Ferrando, release 10.5.03, June 2017) was used to conduct EFA.

Step 2. Item reduction

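### The ten County B homes serve first as controls and then as intervention homes, so measurement history differs between the groups and a person may be counted in both; the between-group analyses allow for neither

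*Protocol*

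**What the plan says.** The Protocol (Updated design of the implementation research) describes a non-randomised controlled trial "implemented over a six-month period in 30 nursing homes in two different counties". Of the first wave it says that "the intervention was implemented in ten nursing homes in County A (Kronoberg County from April 2015"). The comparison homes for that wave came from the other county: "while ten nursing homes in County B served as a control group". Of the second wave it says: "Then, County B implemented the intervention (Skåne county from August 2016), and ten new nursing homes in County A" took the control role. About these added homes it notes: "which had not received the intervention, were chosen as a control group". The two waves were then pooled into one intervention and one control group.

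The section on evaluating the implementation has data collected before and after, at the same time in both groups. In Table 2 the control follow-up is six months for staff and nine months for next of kin. On recruitment, the Protocol (Participants in studies) says: "The persons are selected consecutively until the stipulated figures are reached". It has no rule about people who already took part in the first wave.

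In the SAP (Comparative studies), the Mann-Whitney and Kruskal-Wallis tests are what "was applied to compare the baseline characteristics of the two groups", and before-after change is tested within each group by the Wilcoxon signed rank test. The SAP (Logistic regression studies) adds a univariate staff model relating improvement in P-CAT and PCQ-S to group, with "the dependent variable group (control/implementation"). None of these analyses has a term for home, person or earlier measurement, and no count of people in both groups is planned.

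**The concern.** Two things follow if the same homes supply both groups.

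The first is measurement history. The change between a person's first and second questionnaire can include familiarity with the form, or sensitisation to its topics. P-CAT, the climate questionnaire and the palliative-care experience questionnaire ask about matters close to what is taught. The change from a third to a fourth questionnaire need not contain the same effect. A first-repeat effect would enter the control group's change in full and the intervention group's change only in part.

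The second is double counting. A staff member who answered as a control in 2015 and as an intervention participant in 2016 contributes to both sides of an unpaired comparison. The Mann-Whitney and Kruskal-Wallis tests and the logistic regression treat those two records as coming from unrelated people.

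**Working it through.** **1. Are the County B homes the same in both waves?** Inputs are from the Protocol's design section.
- Same County B homes in both waves: 10 (County A) + 10 (County B) + 10 (new County A) = 30. This reproduces the stated total.
- Different County B homes in the second wave: 10 + 10 + 10 + 10 = 40. This does not.

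**2. Do both control rounds come before the second wave?** Assume a first-wave baseline near April 2015. The last control round then falls at month 6 (staff) to month 9 (next of kin), that is October 2015 to January 2016. August 2016 is month 16, so the gap is 16 - 9 = 7 to 16 - 6 = 10 months. Both rounds come first.

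**3. Home-periods that follow two earlier rounds.**

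| Group | First wave | Second wave | With earlier rounds |
|---|---|---|---|
| Intervention | 10 County A (none earlier) | 10 County B (two earlier) | 10/20 = 50% |
| Control | 10 County B (none earlier) | 10 new County A (none earlier) | 0/20 |

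Ten of the 30 homes (33%) are in both groups.

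**4. Shift in the contrast of changes.** Let p be the share of second-wave County B respondents who also answered in the first wave, and d the excess of the first-repeat effect over the third-to-fourth effect, in SD. If County B supplies half the intervention group, the shift is 0.5 × p × d. The documents give neither p nor d.
- p = 0 or d = 0: shift 0.
- p = 0.3, d = 0.1: 0.5 × 0.3 × 0.1 = 0.015 SD.
- p = 0.8, d = 0.3: 0.5 × 0.8 × 0.3 = 0.12 SD.

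For scale, assume 100 per pooled group and an SD of change of 1. The standard error is then √(2/100) = 0.141, and the largest shift is 0.12/0.141 = 0.85 standard errors. If retesting improves scores, the shift lowers the apparent benefit.

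**5. Effect of double counting on an unpaired test.** Let f be the share of each group made up of people in both (f = p/2 under the equal split), and r the correlation between a person's two records. With equal groups the variance of the difference is multiplied by 1 - f × r, and the true level of a nominal 5% two-sided test is 2Φ(-1.96/√(1 - f × r)). This normal approximation only illustrates the rank tests and the regression. Values of f and r are assumed.

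| f | r = -0.5 | r = -0.25 | r = 0.3 | r = 0.5 | r = 0.7 |
|---|---|---|---|---|---|
| 0 | 5.0% | 5.0% | 5.0% | 5.0% | 5.0% |
| 0.1 | 5.6% | 5.3% | 4.7% | 4.4% | 4.2% |
| 0.25 | 6.5% | 5.7% | 4.2% | 3.6% | 3.1% |
| 0.4 (p = 0.8) | 7.4% | 6.2% | 3.7% | 2.8% | 2.1% |

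Positive r is the natural case for baseline scores, and there the test is conservative. Successive changes in one person can correlate in either direction, so for improvement the level can be too low or too high.

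**The case against.** The strongest reply is that the established fact concerns homes, while the harm needs people. Familiarity with a questionnaire belongs to the respondent. Nothing in the documents says anyone answered in both waves. The waves start 16 months apart, residents are frail, and the Protocol reports more drop-out than expected. This stands: overlap is a possibility, zero is a legitimate lower bound, and for residents it may be close to the truth. It is more plausible among staff, since Table 1 of the Protocol counts all staff of the included homes as implementers and the gap after the last control round is about 7 to 10 months.

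Three stronger conclusions are tempting and are not supported.

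- *That false claims of benefit rise to about 14%.* At the largest shift (0.85 standard errors), a between-group test of mean change would reject 13.6% of the time under no effect. Of that, 13.3 points would be results against the intervention if retesting improves scores, and false benefit would fall from 2.5% to about 0.25%. The SAP also contains no such test, and Table 2 lists only 20 people per group for the interview sub-studies.
- *That the Wilcoxon tests are invalid.* Each pairs a person with themselves within one wave. Overlap between groups does not break that. What suffers is reading one group's change against the other's.
- *That the SAP declares the two trial groups independent.* It uses that word only for the group comparisons in the NoK-PiC psychometric work. In the trial comparison, independence is an assumption of the chosen tests.

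It can also be said that shared homes are simply a clustering problem. That is partly right, and a home term is needed anyway, but it does not represent earlier measurement.

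**Conclusion.** The point holds at two strengths. Reuse of the ten County B homes, and the 10/20 against 0/20 imbalance in measurement history, follow from the Protocol's own count (the order of rounds also assumes a first-wave baseline near April 2015). Double counting of people is possible, not documented, and neither excluded nor handled.

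If there is overlap, p-values from the baseline rank tests and the staff regression are wrong: conservative at baseline under positive within-person correlation, and in either direction for change. The shift in the contrast of changes is 0-0.12 SD for assumed overlap of 0-80% and a retest difference of 0-0.3 SD, against the intervention if the retest effect is an improvement. With no overlap, the double-counting and retest parts vanish, and what remains is that ten homes sit in both groups without a home term.

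Separately, the Protocol's ethical section speaks of two control-only homes where the design section implies ten. These should be reconciled, because the count bears on which homes were reused.

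**What to change.** 1. Link participants across waves, using the study codes or the centrally held list of names where these allow it, and report how many people are in both groups, separately for staff, next of kin and residents. The Protocol mentions codes and a secured list but does not say that codes carry over between waves, so feasibility must be confirmed.
2. Fit the staff analysis with improvement as the outcome and group as the predictor (the SAP has these the other way round), with random effects or GEE clustering for home and, if there is overlap, person, plus a prior-measurement indicator. Code the indicator per person; coded per home it would only mark the second-wave County B homes.
3. As a sensitivity analysis, repeat the between-group and within-group analyses in first-time respondents only.

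The cost is a few lines in the SAP and a linkage step, with no new data, and some loss of precision. The restricted analysis also unbalances county and wave. With 100 per group, an even county split and 80% overlap, County B would fall from 50 to 10 intervention respondents, leaving 50/60 = 83% from County A, while the control group stays at 50/50. That is why it should not be primary. If linkage shows no overlap, a sentence saying so settles the double-counting question.

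### Arm equals county within each wave, yet the waves are pooled with no county or wave term; county and period differences are sure to cancel only if each arm is split evenly across the waves

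*Protocol*

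**What the plan says.** The Protocol (Updated design of the implementation research) describes a non-randomised trial in 30 voluntarily participating homes, run in two waves.

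- Wave 1: "the intervention was implemented in ten nursing homes in County A (Kronoberg County from April 2015"). Its controls were ten County B homes over the same period.
- Wave 2: the intervention moved to County B in August 2016. For the comparison, "ten new nursing homes in County A, which had not received the intervention, were chosen as a control group".
- Analysis: "After the two sequential time periods were data from one intervention and one control group analysed".

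On recruitment, the Protocol (Participants in studies) says: "The persons are selected consecutively until the stipulated figures are reached (Table 2"). No quota by county or wave is given.

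For change over time, the SAP (Comparative studies) names Wilcoxon signed rank tests within each group. The only model linking change to arm is in the SAP's Logistic regression studies, for staff: "A univariate logistic regression analysis was performed with the independent variable improvement/non-improvement in P-CAT and PCQ-S". None of the named analyses has a term or stratum for county, wave or nursing home.

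**The concern.** Homes were not randomised, so the swap of counties between waves is the main design feature that separates the intervention from the county. The plan built this feature in but does not use it in the analysis. The waves also start in different years and seasons: six months on from April 2015 is October, and six months on from August 2016 is February. If one county, or one wave, changes more than the other for reasons unrelated to the intervention, and the arms are unevenly filled across waves, part of that difference is counted as intervention effect. Pooling also hides whether the two waves agree. That matters because wave 2 differs in kind from wave 1: its controls come from a county where the intervention had already been run, and its intervention homes had probably been measured before as controls.

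**Working it through.** **Inputs from the documents.** Ten homes in each of three cells and 30 homes in all (Protocol, Updated design); 100 staff per arm (Protocol, Table 2, sub study 6, which does not say whether per wave or in total); two-sided 0.05 (SAP, Comparative studies). **Assumed,** because the documents give no figures: the wave split, the county and period differences, a change SD of 1, and independent participants.

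**Step 1: homes.** 10 (A, wave 1) + 10 (B, wave 1) + 10 new (A, wave 2) = 30, which reproduces the stated total. That leaves no room for new County B homes, so the wave 2 intervention homes must be the wave 1 County B controls. Four cells of ten make 40 home-by-wave slots filled by 30 homes.

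**Step 2: bias of the pooled contrast.** Let E be the effect, t the wave 1 minus wave 2 difference in change, and c the County A minus County B difference in change. Let pI and pC be the wave 1 shares of the intervention and control participants.

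| Cell | Arm | Mean change |
|---|---|---|
| A, wave 1 | intervention | E + t + c |
| B, wave 1 | control | t |
| B, wave 2 | intervention | E |
| A, wave 2 | control | c |

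Pooled intervention mean = E + pI(t + c). Pooled control mean = pC·t + (1 − pC)c. The difference is

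E + (pI − pC)t + (pI + pC − 1)c.

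With pI = pC = 0.5 both bias terms are zero, whatever t and c are and whatever the arm sizes.

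**Step 3: uneven splits, no true effect.** SE = √(2/100) = 0.141; rejection = Φ(bias/SE − 1.96) + Φ(−bias/SE − 1.96).

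| pI | pC | Assumed difference | Bias (SD) | Rejection, 100 per arm | 200 per arm |
|---|---|---|---|---|---|
| 0.5 | 0.5 | any t, c | 0 | 5% | 5% |
| 0.6 | 0.6 | c = 0.3 | 0.2 × 0.3 = 0.06 | 7.1% | 9.2% |
| 0.6 | 0.4 | t = 0.3 | 0.2 × 0.3 = 0.06 | 7.1% | 9.2% |
| 0.7 | 0.7 | c = 0.3 | 0.4 × 0.3 = 0.12 | 13.6% | 22.4% |

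**Step 4: adjustment.** The equally weighted mean of the two within-wave differences is ½[(E + c) + (E − c)] = E for any split. This is also the arm coefficient when county and wave are in the model. Its cost with 100 per arm:

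- 70/30 in both arms: variance ¼(2/70 + 2/30) = 0.02381 against 0.02, so the SE ratio is √(0.02381/0.02) = 1.09.
- 60/40 in both arms: ¼(2/60 + 2/40) = 0.02083, ratio 1.02.
- Even split: no cost.

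**Step 5: what adjustment cannot do.** Intercept, arm, county and wave are four parameters for four cell means. If County A's change in wave 2 carries an extra x, the adjusted estimate is ½[(E + c) + (E − c − x)] = E − x/2. With x = 0.3 SD the bias is 0.15 SD in size even with equal cells (18.6% rejection at 100 per arm). The interaction is fully aliased with arm.

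**Step 6: the staff logistic model.** Because it is non-linear, equal cells do not cancel shifts exactly. With no effect, baseline log-odds −0.4, and county and period log-odds of 1 each, the pooled improvement proportions are 0.6457 and 0.6167, an odds ratio of 1.13. With 0.5 each it is 1.006, which is negligible.

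**The case against.** The design already does much of the work. Each arm holds one wave from each county, and the Protocol (The evaluation of the implementation) has both arms measured at the same time. The home counts imply ten per cell. Table 2 figures may also be per wave: the Protocol reports the participation questionnaire tested on 400 next of kin, and 100 × 2 arms × 2 waves = 400. The SAP's WHOQOL-BREF sample of next of kin, 240 + 14 = 254, likewise exceeds 200. The Protocol mentions drop-out as a reason for abandoning the cross-over plan, not as evidence of unequal cells afterwards. Finally, the rejection rates above describe a between-arm test of continuous change, which the SAP does not name; it tests change mainly within groups.

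Most of this stands. A reader might infer that pooling alone lets county and period changes into the arm comparison, or that the trial could amount to a plain County A versus County B comparison. The documents support neither: additive shifts cancel under an even split, and both the design text and Table 2 describe data from both waves.

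What remains is that an even split of homes is not an even split of participants analysed. No cell counts are given, and the 400 is only suggestive. The SAP compares drop-outs with participants only within each arm, so a loss concentrated in one wave would go unseen. The within-group tests are no safeguard, since period change enters them directly.

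**Conclusion.** The concern holds in a limited form, as something that should be fixed rather than a fatal flaw. The analysis ignores the county-by-wave structure on which the comparison depends, and whether this biases the result cannot be judged from the documents. Additive bias is zero under an even wave split in each arm. It is about 0.06 SD (about 7% error in place of 5% at 100 per arm) under an assumed 60/40 split in both arms with a 0.3 SD county difference. It would be 0.12 SD at 70/30. The splits and differences are assumptions, and the error rates ignore clustering, so they show scale only. A reader might also infer that adding county and wave makes the comparison free of confounding. It does not, because a county-by-wave interaction remains inseparable from the arm effect. That County B homes sit in both pooled groups is an inference from the 30-home total, not a stated fact.

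**What to change.** - For every arm comparison of change, estimate the arm effect adjusted for county and wave, equivalently the equally weighted mean of the two within-wave intervention-minus-control differences in change.
- Add county and wave to the staff P-CAT and PCQ-S logistic regression, with improvement as the outcome. The SAP labels improvement as the independent variable and group as the dependent one. That does not alter the odds ratio with a single predictor, but it does once covariates enter.
- Show the two within-wave differences separately, and report the number analysed in each of the four county-by-wave cells.
- State that a county-by-wave interaction is aliased with arm and cannot be removed.
- Confirm whether the County B homes served as controls and then as intervention homes; if so, account for the same homes appearing in both pooled groups.

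The Protocol reports the trial in the past tense, so a rule for balanced recruitment would come too late; these are changes to analysis and reporting, and should be dated as such. They need only county and wave, which the trial must already hold. The cost is a slightly larger standard error if cells are unequal: about 2% at 60/40 and 9% at 70/30 in both arms.
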